While the evidence seems to support a relationship between a change in microbiota and NEC, there is no clear relationship between anemia or transfusion and NEC. There have been no studies evaluating the relationship between anemia or transfusion and a change in microbiota. That is the primary focus of this study.

Hypothesis:

Anemia will result in alteration of the stool microbiota. Transfusion will return microbiota to baseline. The specific alteration in microbiota with anemia may include: increase in *Proteobacteria*, decrease in *Firmicutes*, and/or decrease in microbiota diversity.

Primary Outcome:

- Change in microbiota with anemia

Secondary Outcome:

- Change in microbiota after transfusion

Inclusion Criteria:

- Preterm infants less than 32 weeks gestation at birth
- ≥ 7 days and <30 days on enrollment
- On minimum 100mL/kg enteral feeds

Exclusion Criteria:

- NEC prior to enrollment
- Prior surgery
- Major congenital anomalies
- Oxygen requirement with $\text{FiO}_2 > 50\%$

Methods:**Definitions:**

- Severe anemia will be defined as a hematocrit $< 25\%$.
- Anemia will be defined as a hematocrit ≥ 25 and $<30\%$.
- No anemia will be defined as a hematocrit $\geq 30\%$.

Hematocrit will be tested per patient's care team. In this unit, hematocrit is usually obtained every Monday, and sometimes more frequently.

Sample Collection:

- Collect stool samples weekly (Sunday, Monday, or Tuesday)
- Collect stool samples 1, 4, and 7 days post-transfusion
- Stool will continue to be collected until infants are 38 weeks corrected gestational age (CGA) or discharge (whichever is earlier).

Data Collection:

Hematocrit	Gestational Age
Birthweight	Apgars
Sex	Race
Singleton/Multiple	Age at stool collection and at hematocrit blood sampling
Iron supplementation	Type of feeds (breastmilk/formula feed)
Calorie fortification of feeds	Total days on antibiotics
Number of transfusions	Positive cultures
NEC	Indomethacin exposure

Groups:

Paired samples will be obtained from the same infants, one before and one after onset of anemia. Therefore, the patients will serve as their own controls.

Sample Analysis:

- Stool samples obtained while patient is on antibiotics will not be included in analysis since the microbiota is expected to be significantly changed with large populations wiped out. Stool samples obtained 5 days after completion of antibiotics will be included in analysis again since infants are expected to be recolonized by that time.

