- qRT-PCR of samples will be performed to quantify the major bacterial groups: *Proteobacteria*, *Firmicutes*, and *Bacteroides*.
- Next generation sequencing will be done for qualitative analysis and metagenomics profiling of bacteria

Informed Consent:

New admissions to the Parkland NICU will be screened for recruitment if their birth gestational age (OB assigned) is less than 32 weeks 0 days and if they are at least 7 days old.

- If they meet these two criteria, they will be screened to ensure they do not meet exclusion criteria.
- If they do not meet the exclusion criteria, then their feeds will be evaluated. If they are on at least 100mL/kg/day of enteral feeds, then they will be approached for recruitment. Infants that are not yet on 100mL/kg/day of enteral feeds will have their charts assessed daily until 29 days of life. If and when they achieve 100mL/kg/day of enteral feeds, they will be approached for recruitment. If an infant does not achieve 100mL/kg/day of enteral feeds before 30 days of life, they will not be approached for enrollment in this study.
- If an infant meets the above criteria, and once their parent/guardian/LAR provides consent, then stool collection will begin for that infant from the next available defecated diaper. In cases where the patients are not the PI's patients, the study team will inform all the physicians caring for the patients within the NICU about this research study and

once they approve for their patients' (infant's) parents/guardians/LARs to be approached for consenting purpose to enroll the infant into this study, the bedside nurse will check with the parents/guardians/LARs if they would like to be approached. Once they let the beside nurse know if they agree to be approached, the nurse would inform this to [name] (the PI) and [name] (study team) who will be responsible for recruitment of subjects and they would approach the patient's parent/guardian/LAR for consenting purposes.

Sample Size Calculation:

Group sample sizes of 194 achieve 80% power to detect an odds ratio of 1.500 in a design with 2 repeated measurements having a simple covariance structure when the proportion for group 2 is 0.4 and group 1 is 0.5. The alpha level is 0.05.

Statistical Analysis:

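### One stool before and one after onset of anemia cannot separate anemia from age, and leaves the choice of stool open, although dated weekly stools are collected

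*Protocol*

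**What the plan says.** The primary outcome is the change in microbiota with anemia. The Groups section of the protocol defines the comparison: "Paired samples will be obtained from the same infants, one before and one after onset of anemia". It adds: "Therefore, the patients will serve as their own controls".

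The Sample Collection section gathers much more than two stools from most infants:

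- routine stools: "Collect stool samples weekly (Sunday, Monday, or Tuesday";
- around transfusion: "Collect stool samples 1, 4, and 7 days post-transfusion";
- duration: "Stool will continue to be collected until infants are 38 weeks corrected gestational age (CGA) or discharge (whichever is earlier".

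Enrollment is at "≥ 7 days and <30 days on enrollment". Age at stool collection and at hematocrit sampling is on the Data Collection list. The only stools removed by rule are those in the antibiotic window (Sample Analysis): "Stool samples obtained while patient is on antibiotics will not be included in analysis", with stools admitted again 5 days after the course ends. The Statistical Analysis section names ANOVA for repeated measurements without saying how many stools per infant it takes.

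**The concern.** Three consequences follow from the Groups rule as written.

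1. Eligible weekly stools beyond the pair have no place in the primary contrast.
2. Where several stools qualify on either side of onset, one must be chosen on each side, and no rule says which. With three bacterial groups and diversity all of interest, that choice could be made after results are known.
3. The stool after onset is always taken at a later age than the stool before. The protocol's own Background describes a microbiota that only begins to develop at about two weeks, and infants enter between 7 and 29 days. A before/after difference is therefore expected from maturation alone. Serving as one's own control removes stable differences between infants but not this drift.

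The third matters most. A shift in the pair could be reported as an effect of anemia when it is partly or wholly an effect of age.

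**Working it through.** **The plan's own figure.** The Sample Size Calculation gives 194 per group for 0.5 against 0.4, 80% power and alpha 0.05 (two-sided assumed). Two independent proportions need n = [1.960·√(2·0.45·0.55) + 0.842·√(0.25 + 0.24)]² / 0.1² = (1.379 + 0.589)² / 0.01 ≈ 387.3, so 388 observations per group. With two uncorrelated measurements per subject, 388/2 = 194. The figure reproduces as two groups of 194, each measured twice.

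**Weekly stools available.** From day 7 to 38 weeks is 38 − GA − 1 weeks: 13 for birth at 24 weeks, 6 for birth at 31. From day 30 it is 38 − GA − 30/7: 9.7 and 2.7 weeks. These are upper limits, because discharge, antibiotics, transfusion and recovery from anemia all reduce the number. A pair is a minority of the weekly stools for most infants, but not for the latest-enrolled, most mature ones.

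**Why a pair cannot separate age.** Write a stool value as infant level + γ·age (weeks) + δ·(after onset) + error. For a pair g weeks apart, the expected difference is δ + γ·g. If every g is about 1, only δ + γ can be estimated. Two stools on the same side of onset differ by γ per week, with no δ, and so carry the missing information.

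**Precision.** I computed the generalised least squares variance of δ with an infant intercept and autocorrelation ρ between successive weeks, divided by the variance of one adjacent pair, 2(1 − ρ). The protocol gives no ρ and no stool pattern; both are assumed.

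| ρ | 2 before + 4 after, no age | 1 + 2, no age | 2 + 4, linear age | 6 stools, mixed onset, shared age slope |
|---|---|---|---|---|
| 0 | 0.38 | 0.75 | 1.19 | 1.07 |
| 0.3 | 0.61 | 0.88 | 1.42 | 1.33 |
| 0.5 | 0.77 | 0.94 | 1.45 | 1.40 |
| 0.7 | 0.91 | 0.98 | 1.40 | 1.38 |

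Mixed onset means onset spread equally over the five possible positions among six stools.

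By hand at ρ = 0 for 2 + 4:

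- Without age: (1/2 + 1/4)/2 = 0.375.
- With age, at times −2 to 3: the sum of squares of the before/after indicator is 4 − 16/6 = 1.333, that of age is 19 − 1.5 = 17.5, and their cross-product is 6 − 2 = 4. What remains for δ is 1.333 − 16/17.5 = 0.419. The variance is 1/0.419 = 2.386, and 2.386/2 = 1.19.

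In standard-error terms, √1.07 = 1.03 and √1.45 = 1.20, so the age-adjusted interval is about 3% to 20% wider than the unadjusted pair's in these settings. Sparse patterns do worse. If every infant gave only 1 + 2 stools, δ would be estimated by 2·y(0) − y(−1) − y(1), with variance 6 at ρ = 0, and 6/2 = 3.0.

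**The case against.** **Serial collection has its own purpose.** Onset of anemia cannot be foreseen, so weekly stools are needed just to obtain a pair. That stands: collecting more than the primary contrast uses is no contradiction. It does not explain leaving dated stools out of that contrast once they exist.

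**A reader might infer that the remaining stools are thrown away.** The protocol does not say so. Its only exclusion by rule is the antibiotic window, post-transfusion stools serve the secondary outcome, and the ANOVA sentence is not limited to two measurements. What the text supports is narrower: the Groups rule gives these stools no role in the before/after comparison.

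**A reader might take the sample size, "in a design with 2 repeated measurements having a simple covariance structure", as confirming the one-pair rule.** It does not. The 194 reproduces with two measurements within each of two groups, not one on each side of onset.

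**A reader might infer a large gain in power**, for instance 194/0.375 ≈ 517 equivalent pairs. That holds only with no age term, independent weekly errors and 2 + 4 usable stools. Nothing in the documents shows that four later stools would typically still be anemic and untransfused. With age in the model, the ratio passes 1.

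**Analysis detail may be left to a SAP**, which is not shown. Pair selection and model form could well be settled there. The limit of one stool on each side, however, is fixed in the protocol itself.

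**Pairs with varied gaps** could identify age in principle. That relies on accidental gap variation and extrapolation to a gap of zero, a weak basis when direct evidence on age is already collected.

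**Conclusion.** The point holds as a worthwhile and inexpensive improvement; it is not a wrong figure or an internal contradiction. The one-before/one-after rule confounds anemia with age when pairs are adjacent, and it leaves stool selection open.

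Using all eligible stools does not promise a smaller variance once age is included. The ratio to the unadjusted pair is about 1.1 to 1.45 in the two six-stool settings above, and larger with few stools per infant. The comparison is not like for like, since the unadjusted pair estimates anemia plus a week of maturation. For adjacent pairs, an age-adjusted effect cannot be estimated at all. The ratios of 0.38 to 0.91 (2 + 4) and 0.75 to 0.98 (1 + 2) apply only if age is left out.

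Assumptions: weekly autocorrelation 0 to 0.7, the stool patterns shown, a linear age trend (shared across infants in the mixed-onset case), and within-infant information only. A random infant effect may recover some between-infant information, which was not computed. Age adjustment removes drift only as far as the age term is adequate, and it does not deal with other changes over time, such as feeds.

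**What to change.** Reword the Groups rule along these lines: all eligible weekly stools of an infant before onset of anemia and, while the infant is still anemic and untransfused, after onset are analysed in one model with infant as a random effect, serial correlation between successive stools, and age at stool as a covariate. Keep the single pair as a sensitivity display, and state in advance which stool is taken on each side (for example, the nearest eligible one).

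The cost is a change of wording plus assays of additional stools already collected, if only pairs were budgeted. The team should also expect a wider interval than the unadjusted pair would give. No change to collection is needed, since the weekly stools and the age at each are already planned.

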Study Title: Alteration of Stool Microbiota in Preterm Infants Less than 32 Weeks with Anemia, and Following Blood Transfusion

Date Approved by IRB: November 22, 2017

The University of Texas Southwestern Medical Center at Dallas
Institutional Review Board

Study Title:

Alteration of Stool Microbiota in Preterm Infants Less than 32 Weeks with Anemia, and Following Blood Transfusion

Investigators:

[name]

[name] (PI)

Type of Funding:

Institutional

Purpose:

- To determine if the stool microbiota in preterm infants is altered with anemia.
- To determine if the stool microbiota in preterm infants is altered after blood transfusion.

Background:

Neonatal gut microbiota begins developing at approximately 2 weeks of age and is less diverse than the microbiota of a term infant. Four bacterial classes make up more than 90% of the microbes present in the neonate: *Bacilli*, *Gammaproteobacteria*, *Clostridia*, and *Negativicutes*. There are multiple factors that influence the neonatal gut microbiota, including mode of infant delivery, type of feeds (i.e. formula or breast milk), medications such as antibiotics, and exposure to pathogens in a hospital environment.

Dysbiosis occurs when there is an imbalance in the proportion of bacterial pathogens and commensal bacteria. This can cause a shift away from homeostasis and lead to an inflammatory state and disease. Studies utilizing molecular methods suggest that dysbiosis occurs in neonates with necrotizing enterocolitis (NEC). While results vary, large studies and meta-analyses suggest a predominance of *Gammaproteobacteria* with NEC and a decrease in *Firmicutes* with NEC. There may also be a decrease in bacterial diversity prior to NEC onset.

The relationship between transfusion and necrotizing enterocolitis has been controversial and frequently studied. Despite this, there is a lack of good quality studies on this topic with conflicted findings and the literature does not currently support a relationship between transfusions and NEC. There have been limited studies on the relationship between anemia and NEC. Some suggest that severe anemia and NEC are associated, however this has not been shown in other studies.

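### Own-control pairing does not control type of feeds, which can change between the stool before and the stool after onset of anemia; date feeds to each stool and add a feed-aware analysis

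*Protocol*

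**What the plan says.** The Groups paragraph of the protocol's Methods sets up the primary comparison: "Paired samples will be obtained from the same infants, one before and one after onset of anemia". It then draws the conclusion at issue: "Therefore, the patients will serve as their own controls".

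The Background lists influences on the neonatal gut microbiota, "including mode of infant delivery, type of feeds (i.e. formula or breast milk), medications such as antibiotics" among them. Feeds and antibiotics thus stand in the same sentence as causes of microbiota change.

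The Inclusion Criteria require at least 100 mL/kg of enteral feeds. The Informed Consent section shows that this is checked up to the approach for consent, and nothing fixes feeds afterwards. Sample Collection continues weekly, and after transfusions, to 38 weeks corrected age or discharge, whichever is earlier.

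The Data Collection list includes type of feeds, "Calorie fortification of feeds" and "Iron supplementation" without any timing. The one timed entry is "Age at stool collection and at hematocrit blood sampling".

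Sample Analysis drops stools taken during antibiotics and readmits them five days after the course ends. Statistical Analysis names chi-square or Fisher tests, t or Mann-Whitney tests and ANOVA for repeated measurements, with no covariate.

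**The concern.** A within-infant comparison cancels sex, race, gestation at birth and mode of delivery, because each infant carries the same value into both stools. It does not cancel anything that differs between the two stools. Feed type is such a factor, and the protocol itself says that it shapes the microbiota.

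If an infant moves between breast milk and formula after the first stool and before the second, the effect of that move enters the paired difference in full. The analysis as described has no means of telling it from an effect of anemia. The primary outcome, change in microbiota with anemia, is at stake. A feed effect could create an apparent anemia effect, enlarge a real one or mask it.

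**Working it through.** **1. Two named influences, treated differently.**

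| | Antibiotics | Type of feeds |
|---|---|---|
| Named in Background as an influence | yes | yes |
| Can differ between the two stools | yes | yes |
| Rule on which stools are used | yes (Sample Analysis) | none |
| Adjustment named in Statistical Analysis | none | none |
| Removed by pairing | no | no |

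**2. Time available for a change.** Entry is at day 7 to 29 of life, for births below 32 weeks. At the 32-week boundary, follow-up to 38 weeks is (38 − 32) × 7 = 42 days from birth. That leaves 42 − 29 = 13 days for the latest entrant and 42 − 7 = 35 days for the earliest. It is longer for lower gestations and shorter if discharge comes first. Stools are weekly, so a pair may be only about a week apart, but the protocol does not fix the interval.

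**3. The protocol's own figure.** For 0.5 versus 0.4, two-sided 0.05 and 80% power, the two-proportion formula gives 388 per group. With 2 measurements per infant and simple covariance read as within-infant correlation ρ = 0, 388 × (1 + 0)/2 = 194. The stated 194 is reproduced and is not in dispute. The odds ratio is (0.5/0.5)/(0.4/0.6) = 1.5, as stated.

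**4. Illustration of the bias.** None of the following inputs except 0.4, 194 and 0.05 appears in the protocol, and reading 194 as the number of pairs is itself an assumption. Suppose anemia has no effect and the proportion before is p1 = 0.4. A share s of infants changes feeds between the two stools, and each change raises the proportion by e. Then:

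- p2 = 0.4 + s × e, so the spurious difference is d = s × e.
- With independent outcomes within an infant, the discordant probabilities are (1 − p1) × p2 and p1 × (1 − p2).
- Under a McNemar-type test, the critical difference is 1.96 × √(sum of the discordant probabilities / 194).

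One case in full, s = 0.2 and e = 0.2: p2 = 0.44. The discordant probabilities are 0.6 × 0.44 = 0.264 and 0.4 × 0.56 = 0.224, with sum 0.488 and difference 0.04. The critical difference is 1.96 × √(0.488/194) = 0.098. The probability of rejection is 12.5%.

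| s | e | Spurious difference | Apparent OR | False-positive rate |
|---|---|---|---|---|
| 0.1 | 0.1 | 0.01 | 1.04 | 5.5% |
| 0.2 | 0.2 | 0.04 | 1.18 | 12.5% |
| 0.3 | 0.3 | 0.09 | 1.44 | 42.7% |
| 0.5 | 0.2 | 0.10 | 1.50 | 50.4% |

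The last row equals the whole effect for which the study was sized. Its rejection rate is near 50% rather than 80% because 194 pairs give 194 observations per state, whereas the protocol's calculation has two measurements on each of 194 infants per group. The table assumes that all feed changes act in the same direction. Changes in opposite directions would partly cancel and add noise instead.

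**The case against.** Four objections deserve an answer.

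- **Timing of the data.** A reader might infer that feed status at each stool cannot be recovered. The protocol does not support that. Data Collection is a bare list of variable names and nowhere says that feeds are recorded once per infant. It is also plainly not a full specification of timing: the antibiotic rule and the post-transfusion stools need dates, yet the list shows only a total of antibiotic days and a count of transfusions. What stands is that the protocol does not require feed type to be tied to a stool.
- **Iron and fortification.** A reader might put these on a level with feeds, or suppose that iron starts in response to a low hematocrit. No section says that either affects the microbiota or that iron follows hematocrit. Only feed type is named as an influence.
- **The analysis plan.** Pair selection and covariates are often left to a SAP, which may exist. Repeated-measures ANOVA does not exclude covariates. This is fair, but adjustment in any SAP would need feed status at each stool, and the protocol presents pairing as its control.
- **Over-correction.** Limiting the primary analysis to feed-concordant pairs could be costly. If 20% to 50% of 194 pairs were lost (194 × 0.2 ≈ 39; 194 × 0.5 = 97), nominal 80% power would fall to roughly 71% to 51%, and the remaining infants might be unrepresentative. Adjusting for iron could over-adjust if it tracks anemia closely. Both points stand, and the fix respects them.

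**Conclusion.** The concern holds for type of feeds. The protocol relies on pairing for the primary comparison, pairing does not remove an influence that the protocol itself names, and neither a stool rule nor a stated adjustment takes its place. A feed change between the two stools therefore cannot be separated from an anemia effect under the stated design and tests.

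The size and direction of the bias cannot be computed from the protocol, which gives neither the frequency of feed changes nor their effect. The illustration shows only that the bias can range from negligible to the full design effect. A reader might want to quote a fixed percentage inflation of the anemia effect; any such figure would rest on invented inputs. Nor does the protocol show that bias will occur, since pairs may be close in time and on the same feeds. This is a worthwhile, inexpensive improvement; it does not by itself invalidate the design.

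**What to change.** 1. State in the protocol that feed type is recorded at each stool date, together with the fortification and iron status already on the list.
2. Where an infant has several eligible stools, use the before/after pair closest in time with the same feed type. Set this rule before microbiota results are seen. Keep every infant in the primary analysis, including those without a same-feed pair.
3. Add either a within-infant analysis with feed type at the stool as a time-varying term, or a sensitivity analysis limited to pairs with unchanged feeds.
4. Report fortification and iron status at each stool descriptively or in sensitivity analyses only, since iron may be close to collinear with anemia.
5. Qualify the own-control sentence: pairing controls for factors fixed within the infant, and feeds are handled by the steps above.

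The cost is slightly more chart abstraction and a sensitivity analysis less precise than the primary one. No infant leaves the primary analysis. The change concerns recording and analysis only, not feeding or iron practice.

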Descriptive analysis will use percentages, means, medians, and measures of variability to describe demographic data. Categorical factors will be evaluated using Chi-square or Fisher exact test between the groups. Continuous factors will be evaluated using Student's t-test or Mann-Whitney U test if the data is non-normal distributed between the groups. Repeated measurements will use analysis of variance (ANOVA) to compare groups. The statistical significance level will be 0.05 for all statistical tests.

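### The 194-per-group, 80% power statement belongs to a two-group comparison of an unnamed proportion, not to the planned before/after comparison within infants

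*Protocol*

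**What the plan says.** The sizing statement (Protocol, Sample Size Calculation) reads: "Group sample sizes of 194 achieve 80% power to detect an odds ratio of 1.500 in a design with 2 repeated measurements", continuing "having a simple covariance structure when the proportion for group 2 is 0.4 and group 1 is 0.5". Alpha is 0.05, with sidedness not stated.

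The design is set out under Groups: "Paired samples will be obtained from the same infants, one before and one after onset of anemia". The next sentence draws the consequence: "Therefore, the patients will serve as their own controls".

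Three other places bear on what is being sized:

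- Primary Outcome: "Change in microbiota with anemia", with no measure or event attached.
- Sample Analysis: "qRT-PCR of samples will be performed to quantify the major bacterial groups", with sequencing in addition.
- Statistical Analysis: "Repeated measurements will use analysis of variance (ANOVA) to compare groups".

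**The concern.** The sizing sentence speaks of two groups with two proportions and repeated measurements within each. The design section describes a single cohort in which each infant contributes one sample to each state. These are different designs, and their variances depend on the within-infant correlation in opposite ways. In a two-group comparison with repeated measurements, positive correlation lowers power. In a paired comparison, it raises power. A calculation that sets the correlation to zero for the first design says little about the second.

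The proportions 0.5 and 0.4 are also tied to no event, while the laboratory work yields quantities of bacterial groups. And the wording leaves open whether 194 or 388 infants are to be enrolled.

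This sentence is the only justification given for how many preterm infants to recruit. If its 80% is not a property of the primary comparison, a null result cannot be interpreted against it, and nobody can tell whether the recruitment target is too small or larger than necessary.

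**Working it through.** **Inputs from the protocol (Sample Size Calculation):** 194 per group; proportions p1 = 0.5 and p2 = 0.4; odds ratio 1.500; two measurements; simple covariance; alpha 0.05; power 80%. **Assumed:** a two-sided test, and any before/after correlation ρ, since none is given.

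**Step 1. Reproduce the stated figure.**

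The odds ratio is (0.5/0.5)/(0.4/0.6) = 1.5, as stated.

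For two independent proportions with pooled variance under the null, the observations needed per group are

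n = [1.960·√(2·0.45·0.55) + 0.842·√(0.5·0.5 + 0.4·0.6)]² / 0.1² = 387.3.

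With two measurements per infant, the infants needed per group are 387.3·(1 + ρ)/2. At ρ = 0 this is 193.7, i.e. 194. The unpooled variant gives 384.6/2 = 192.3 and the log-odds-ratio variant 389.9/2 = 194.9. A one-sided test gives about 153.

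So 194 is the size of each of two separate groups, with every infant measured twice and simple covariance meaning zero within-infant correlation. Even in that design the 80% depends on the zero: power with 194 per group falls to 69% at ρ = 0.3 and 63% at ρ = 0.5.

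**Step 2. Power of the planned paired comparison, keeping 0.5 against 0.4.**

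With one sample per state in each infant, the corresponding test for a binary outcome is McNemar's:

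- P(event in both samples): p11 = 0.2 + ρ·√(0.25·0.24)
- Discordant proportion: pd = 0.9 − 2·p11
- Pairs needed: N = [1.960·√pd + 0.842·√(pd − 0.1²)]² / 0.1²
- Power: Φ{[0.1·√N − 1.960·√pd] / √(pd − 0.1²)}

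The largest ρ these margins allow is 0.816.

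Example at ρ = 0.5: p11 = 0.2 + 0.1225 = 0.3225 and pd = 0.255. With 194 pairs, (1.393 − 0.990)/0.495 = 0.814, so power is 79%.

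| Assumed ρ | pd | Power, 194 pairs | Power, 388 pairs | Pairs for 80% |
|---|---|---|---|---|
| 0 | 0.500 | 50.4% | 79.8% | 391 |
| 0.3 | 0.353 | 65.2% | 91.5% | 275 |
| 0.5 | 0.255 | 79.2% | 97.6% | 198 |
| 0.6 | 0.206 | 87.2% | 99.3% | 160 |
| 0.7 | 0.157 | 94.6% | 99.9% | 121 |

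With 194 pairs, 80% is reached at ρ of about 0.51. Simulation with 200,000 runs per setting agrees with these powers to within 0.02.

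**Step 3. Can the two groups be read as the before and after states?**

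That does not rescue the sentence. The calculation needs 388 observations per state. With one sample per state, 194 infants supply 194, and at the calculation's own zero correlation the power is 50%. Reading the total as 388 infants, each with a pair, does return 80% at ρ = 0. But the protocol does not state 388, and zero correlation sits badly with using infants as their own controls.

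**Step 4. What the number counts.**

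The Inclusion Criteria do not require that an infant later becomes anemic, and under Sample Analysis "Stool samples obtained while patient is on antibiotics will not be included in analysis". Infants enrolled and infants with a usable pair can therefore differ. The sizing sentence does not say which it means.

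**The case against.** The strongest reply is that no shortfall has been shown. The arithmetic of 194 is correct. The unfavourable figures rest on a correlation and a test that the protocol does not state. Taken literally, two groups of 194 make 388 infants, and if each gave an evaluable pair, McNemar power would be about 80% at zero correlation and higher at any positive one. All of this stands. The 50% figure combines the smaller total with zero correlation and is not the expected case.

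Second, the Statistical Analysis section also plans between-group tests, so the sizing sentence does not stand alone in its two-group language. That is true, but no section defines a second group of infants, and the Groups paragraph is explicit that the contrast is within infant.

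Third, details about evaluable pairs may be in an analysis plan that is not shown, and the antibiotic rule removes samples rather than infants: stool is collected weekly, and samples re-enter five days after a course ends. This is fair, and those remarks are secondary. They do not affect the main point, which is visible within the protocol itself: the sizing sentence and the design section describe different comparisons, and the two proportions belong to no named event.

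**Conclusion.** The concern holds. The figure of 194 is correctly computed, but for a different design, so the 80% power is unsupported for the planned paired comparison. This is a mismatch between design and calculation, not a slip in arithmetic.

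The direction of the error is not established. If 0.5 against 0.4 is a meaningful paired contrast, 194 pairs give anything from 50% to 95% power for an assumed correlation of 0 to 0.7, and the pairs needed for 80% run from 391 down to 121. With 388 pairs, power is about 80% or higher at any non-negative correlation. The closeness to 80% with 194 pairs at a correlation near 0.5 is a coincidence, because the stated calculation uses none. If the outcome is a quantity and not a yes/no event, none of these figures applies directly, and the power depends on the SD of the within-infant change. The correction is needed because the recruitment target rests on this sentence alone.

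**What to change.** Replace the sentence under Sample Size Calculation with a within-infant calculation for a named primary measure. Suggested wording, for the sponsor to complete:

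> [N] infants with an evaluable before/after pair give [x]% power (two-sided 0.05) to detect a mean within-infant change of [target, with justification] in [named measure], assuming an SD of the paired differences of [SD, with source].

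If a binary outcome is intended, define the event to which 0.5 and 0.4 refer, and give McNemar power with a stated correlation or discordant proportion. In either case, say whether the total is 194 or 388 infants and that it counts infants with an evaluable pair, then restate the power or detectable change which that number delivers.

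For orientation only: with a paired t-test, 80% power corresponds to a mean change of about 0.20 SD of the paired differences with 194 pairs and about 0.14 SD with 388. Whether either is a relevant target is for the sponsor to justify.

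The cost is one recalculation and a rewritten sentence. The stated power may become less favourable, and the number of infants to enrol may have to change.
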